8.1.3 Off-study evaluations

These must be performed 28 days (\pm 3days) after the last dose of CCT3833, and should include the following as a minimum:

- Assessment of AEs and concurrent medications.
- ECOG Performance status.
- Physical examination and weight.
- Vital signs.
- Blood tests (including for tumour markers, if applicable).
- ECG.
- Radiological/clinical disease assessment.

8.1.4 Subsequent follow-up

During Part A (the dose escalation phase), if any AEs and SAEs are considered to have a possible – highly probable relationship to CCT3833, and are still present at the Off-study visit, then the patient will be followed up on a monthly basis until resolution to baseline or stabilisation of the events, unless another anti-tumour treatment is started.

For those Part A patients without any ongoing AEs, no further follow-up will be performed after the Off-study visit.

8.2 Part B (dose expansion stage)

8.2.1 Pre-treatment evaluations

8.2.1.1 Baseline evaluations

The following must be performed/obtained between Day -28 and Cycle 1 Day 1:

- Written informed consent.

- Demographics.
- Medical history.
- Availability of historical tumour biopsy (for confirmation of mutation status).
- Height and ECOG performance status.
- Recording of symptoms.
- Review of concurrent medications.
- Echocardiogram (within 28 days of Day 1).
- Radiological imaging (within 28 days of Day 1).
- Tumour biopsy – optional.

The following must be performed between Day -7 and Cycle 1 Day 1:

- Physical examination.
- Clinical disease assessment (if applicable).
- Performance status, weight and vital signs.
- Laboratory investigations: including full blood count, APTT, PT, urea, sodium, potassium, creatinine, ALT, AST, albumin, total protein, total bilirubin, alkaline phosphatase, calcium, LDH, creatine kinase, ESR, CRP, glucose, HbA1c, troponin I, magnesium and phosphate, tumour markers (as appropriate).
- Urinalysis (bHCG).
- ECG.

Baseline imaging must document all areas of disease present (even if specific lesions are not going to be followed for response) and the measurements of all measurable lesions must be recorded clearly. Any non-measurable lesions must be stated as being present. For clinical measurements, documentation by colour photography, including a ruler to estimate the size of the lesion, is strongly recommended.

All radiological assessments must be performed between Day -28 and before starting treatment. The interval between the last anti-cancer therapy and these measurements must be at least 28 days. All clinical measurements to assess response must be done within 7 days before the patient starting treatment. Tumour lesions that are situated in a previously irradiated area can be included as measurable disease if they are clearly progressing at the time of initiating systemic therapy.

8.2.2 On-treatment assessments

8.2.2.1 *Safety and tolerability assessments*

Clinical review

Patients will be clinically reviewed on Cycle 1 Day 1 (\pm 1day). The review will be repeated on Cycle 1 Day 15 (\pm 1day) and then again on Cycle 2 Day 1 (\pm 1day). If no DLTs

are encountered, the visit frequency will be monthly (± 1 day) thereafter (i.e. Cycle 3 Day 1, Cycle 4 Day 1) until disease progression.

Physical examination

A complete physical examination (including skin review) should be performed on Day 1 (± 1 day) of each study cycle, and at the end of treatment. Additional examinations may be performed at the Investigator's discretion if clinically indicated.

Weight

This will be measured on Day 1 (± 1 day) of each cycle and at the end of treatment

Vital signs

Vital signs will be measured as per the clinical review schedule outlined above, and at the Off-study visit.

Laboratory evaluations

Full haematological and biochemical analysis (as described at baseline) should be performed as per the clinical review schedule:

- Cycle 1 Day 1 (± 1 day), and Day 15 (± 1 day).
- Cycle 2 Day 1 (± 1 day) and Day 1 (± 1 day) of all subsequent cycles (assuming no DLTs encountered in expansion phase).
- End of treatment.

ECG

Single standard ECGs will be performed as per the clinical review schedule, with specific review of the QTc interval using Frederica's correction.

Echocardiography

This will be performed after 1 month (± 3 days) on treatment to evaluate for any evidence of LV dysfunction. Thereafter, no routine echocardiography is scheduled, but may be performed as clinically indicated.

8.2.2.2 *Efficacy assessment*

All patients who meet the eligibility criteria, receive at least two cycles of CCT3833, and have a baseline assessment of disease at the end of Cycle 2, will be evaluable for response. Efficacy will be evaluated using CT scans of the chest/abdomen/pelvis, performed every 8 weeks, or more frequently when clinically indicated. Clinical disease assessments should be performed every 4 weeks.

All lesions measured at baseline must be measured at every subsequent disease assessment, and recorded clearly. All non-measurable lesions noted at baseline must be subsequently noted as present or absent. At baseline, a brain CT or MRI must be

performed to assess for brain disease. If treated/stable brain metastases are documented at baseline, brain imaging should be continued throughout the study.

All patients who are removed from the study for reasons other than PrD, must be re-evaluated at the time of treatment discontinuation, unless a tumour assessment was performed within the previous 4 weeks.

All patients discontinuing the study for PrD should have their disease progression documented by radiological evaluation. If a tumour biopsy is to be completed, the biopsy should be completed prior to radiological assessment.

To be assigned a status of CR or PR, changes in tumour measurements must be confirmed by repeat measurements performed no less than 4 weeks after the response criteria are met. To be assigned a status of SD, follow-up measurements must have met the SD criteria at least once, and at least 6 weeks after the first dose of CCT3833 has been taken. Should rapid tumour progression occur before the completion of two cycles of CCT3833 treatment the patient will be classified as having early progression (EP). Tumour response should be classified as “not evaluable” (NE), only when it is not possible to classify it under another response category, for example, when baseline and/or follow-up assessment is not performed or not performed appropriately.

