5.5 Patient evaluability

All patients who meet the eligibility criteria and receive at least one administration of CCT3833 will be evaluable for safety.

Patients who receive less than 75% of the planned doses of CCT3833 during the first treatment cycle (for reasons other than toxicity) will not be evaluable for dose review decisions. Patients who are not evaluable may be replaced.

All patients who meet the eligibility criteria, receive at least 75% of the planned doses of CCT3833 in the first treatment cycle, and have a baseline assessment of disease will be evaluable for disease response according to the RECIST criteria v1.1 (Appendix 5). To be assigned a status of complete response (CR) or partial response (PR), changes in tumour measurement must be confirmed by repeat measurements performed no less than 4 weeks after the response criteria are met. To be assigned a status of stable disease (SD), follow-up measurements must have met the SD criteria at least once, and at least 6 weeks after the first dose of CCT3833 has been taken.

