Thereafter, ECGs will be performed as per the clinical review schedule outlined in Table 12, with specific review of the QTc interval using Frederica's correction.

Echocardiography

This will be performed after 1 month (± 3 days) on treatment to evaluate for any evidence of LV dysfunction. Thereafter, no routine echocardiography is scheduled, but may be performed as clinically indicated.

8.1.2.3 *Efficacy assessment*

All patients who meet the eligibility criteria, receive at least two cycles of CCT3833 and have a baseline assessment of disease and assessment of disease at the end of Cycle 2 will be evaluable for response. Efficacy will be evaluated using CT scans of the chest/abdomen/pelvis performed after 8 weeks of being on a stable dose, or more frequently, when clinically indicated. If patients undergo intra-patient dose escalation, the interval between scans may exceed 8 weeks in order to ensure a period of 8 weeks on a stable dose has been established. Clinical disease assessment should be performed every 4 weeks.

All lesions measured at baseline must be measured at every subsequent disease assessment, and recorded clearly. All non-measurable lesions noted at baseline must subsequently be noted as present or absent.

All patients, who are removed from the study for reasons other than PrD, must be re-evaluated at the time of treatment discontinuation, unless a tumour assessment was performed within the previous 4 weeks.

All patients discontinuing the study for PrD should have their disease progression documented by radiological evaluation. If a tumour biopsy is to be completed, the biopsy should be completed prior to radiological assessment.

To be assigned a status of CR or PR, changes in tumour measurements must be confirmed by repeat measurements performed no less than 4 weeks after the response criteria are met. To be assigned a status of SD, follow-up measurements must have met the SD criteria at least once, and at least 6 weeks after the first dose of CCT3833 has been taken. Should rapid tumour progression occur before the completion of two cycles of CCT3833 treatment, the patient will be classified as having early progression (EP). Tumour response should be classified as "not evaluable" (NE), only when it is not possible to classify it under another response category, for example, when baseline and/or follow-up assessment is not performed or not performed appropriately.

8.1.2.4 *Biomarker assessment*

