Note: Subjects with a global deterioration of health status requiring discontinuation of treatment without objective evidence of disease progression at that time should be classified as having "symptomatic deterioration." Objective response status is determined by evaluations of disease burden. Every effort should be made to document the objective progression even after discontinuation of treatment.

In some circumstances, it may be difficult to distinguish residual disease from normal tissue. When the evaluation of CR depends on this determination, it is recommended that the residual lesion be investigated (fine needle aspirate/biopsy) to confirm the CR.

Evaluation of best overall response

The best overall response is the best response recorded from the start of the treatment until disease progression/recurrence and will be determined programmatically by GSK based on the Investigators assessment of response at each time point.

To be assigned a status of SD, follow-up disease assessment must have met the SD criteria at least once after first dose at a minimum interval of 4 weeks.

If the minimum time for SD is not met, best response will depend on the subsequent assessments. For example if an assessment of PrD follows the assessment of SD and SD does not meet the minimum time requirement the best response will be PrD. Alternative subjects lost to follow-up after an SD assessment not meeting the minimum time criteria will be considered not evaluable.

Confirmation criteria (recommended):

To be assigned a status of PR or CR, a confirmatory disease assessment should be performed no less than 4 weeks (28 days) after the criteria for response are first met.

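### The protocol gives conflicting response-evaluable rules and names no denominator, so the reported response rate could be inflated by leaving out early failures

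*Combined protocol and SAP*

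**What the plan says.** Three sections define who counts for response.

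- **Section 8.1.2.3 (Part A).** Eligible patients must "receive at least two cycles of CCT3833 and have a baseline assessment of disease and assessment of disease at the end of Cycle 2".
- **Section 8.2.2.2 (Part B).** Eligible patients who "receive at least two cycles of CCT3833, and have a baseline assessment of disease at the end of Cycle 2, will be evaluable for response". Taken literally, this asks for a baseline assessment eight weeks into treatment, which cannot be applied. Some words present in the Part A sentence appear to have been lost.
- **Section 5.5 (whole trial).** Eligible patients who "receive at least 75% of the planned doses of CCT3833 in the first treatment cycle, and have a baseline assessment of disease" are evaluable. Neither a second cycle nor an end-of-Cycle-2 scan is needed.

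Sections 8.1.2.3 and 8.2.2.2 also give patients who progress rapidly before finishing two cycles their own category, early progression (EP). They allow the not-evaluable category (NE) "only when it is not possible to classify it under another response category". Patients who come off for reasons other than progression "must be re-evaluated at the time of treatment discontinuation", unless a tumour assessment was done in the preceding 4 weeks.

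Section 10.3.4 presents best response as proportions and puts the first response assessment at 8 weeks. It does not state the denominator or say how EP and NE are counted. Section 9.6.1 defines early death, but no section gives such a patient a response category. Section 6.13 provides for no replacement in Part B, and Section 10.3.5 evaluates each melanoma cohort separately.

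On stable disease (SD), Sections 5.5, 8.1.2.3 and 8.2.2.2 require at least 6 weeks from first dose. Appendix 5 requires patients to have met "the SD criteria at least once after first dose at a minimum interval of 4 weeks".

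**The concern.** A patient who progresses, dies or stops for toxicity before week 8 is a treatment failure. The evaluability rule in Section 8, used as a denominator, would remove that patient. The same sections classify such a progressor as EP, so their two provisions pull against each other.

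Section 5.5 is looser but has the same weakness, because it too conditions on exposure after baseline. Its dose-review sentence exempts shortfalls caused by toxicity; its response sentence does not. A patient who dies or stops for toxicity early in Cycle 1 is therefore outside both response sets.

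The exclusions would act in one direction. With the first scheduled assessment at 8 weeks and confirmation of complete or partial response (CR/PR) at least 4 weeks later, patients lost before week 8 would almost all be non-responders. In an unreplaced cohort of 9, each one removed shifts the proportion visibly. With the denominator left open, the choice could also be made after the data are seen.

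Response is a secondary endpoint, but it has uses. Section 2.1 looks to Part B for early efficacy signals and for support in designing later trials, and Section 6.5 allows demonstrated efficacy to inform the recommended Phase 2 dose.

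**Working it through.** **Plan's own figures.** Section 10.2 gives 3 cohorts of 9: 3 × 9 = 27. Adding the Part A maximum, 42 + 27 = 69, as in Section 2.1. Both reproduce. The documents give no target response rate, dropout rate, alpha or power.

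**Inputs for the check**

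- n = 9 treated per cohort (Section 10.2), ignoring any Part A patients carried over under Section 6.9.3.
- x = number of responders: an assumption, shown for 1, 2 and 3.
- k = number of early non-responders removed by the evaluability rule: an assumption, shown for 0 to 3.

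**Formulas.** Rate in all treated patients = x/n. Rate in the evaluable set = x/(n − k). Inflation factor = [x/(n − k)] / [x/n] = n/(n − k), which does not depend on x.

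| k dropped | Factor | x = 1 | x = 2 (exact 95% CI) | x = 3 |
|---|---|---|---|---|
| 0 | 9/9 = 1.00 | 1/9 = 11.1% | 2/9 = 22.2% (2.8 to 60.0) | 3/9 = 33.3% |
| 1 | 9/8 = 1.125 | 1/8 = 12.5% | 2/8 = 25.0% (3.2 to 65.1) | 3/8 = 37.5% |
| 2 | 9/7 = 1.29 | 1/7 = 14.3% | 2/7 = 28.6% (3.7 to 71.0) | 3/7 = 42.9% |
| 3 | 9/6 = 1.50 | 1/6 = 16.7% | 2/6 = 33.3% (4.3 to 77.7) | 3/6 = 50.0% |

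Intervals are Clopper-Pearson.

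**The rules side by side.** On once-daily dosing, 75% of a 28-day cycle is 0.75 × 28 = 21 doses. Take 2 responders and 3 early failures, one stopping before 21 doses and two stopping after 21 doses but before the end of Cycle 2 (assumed for illustration):

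- all treated: 2/9 = 22.2%;
- Section 5.5: one dropped, 2/8 = 25.0%;
- Section 8: three dropped, 2/6 = 33.3%.

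If EP, early deaths and NE are kept as non-responders, the rate is 2/9 whichever section is cited.

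**Stable disease.** The gap between 4 and 6 weeks affects only assessments falling in that window. Routine scans start at week 8, so these would be unscheduled scans or re-evaluations at discontinuation. SD is not a response, so the CR/PR rate cannot change.

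**The case against.** A reader might infer that the plan evaluates response only in two-cycle completers, and so does drop early progressors and inflate the rate in every cohort. The documents do not support that. EP is a response category in its own right, NE is a last resort, Section 5.5 admits patients who never reach week 8, and Section 10.3.4 fixes no denominator. A table of best response that keeps EP and NE rows over all treated patients would be consistent with much of the text and would show no inflation. A cohort with no early losses would show none either.

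The size is also uncertain. No early-stop rate is given. Section 4.2.1 requires ECOG 0 or 1 and a life expectancy of at least 12 weeks, conditions that Section 4.2.2 carries into Part B, so 0 or 1 early losses must be among the cases shown. The intervals for 2/9 and 2/6 overlap almost entirely. Response is secondary, Section 10.2 states that no formal hypothesis is tested, and Section 6.5 attaches no response proportion to its mention of efficacy. With 9 patients per cohort, individual outcomes can be listed and either rate recalculated.

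Those arguments limit the claim and its weight. They do not remove the contradiction between Section 5.5 and Section 8, the garbled Part B sentence, the missing denominator, or the absence of a category for a patient who dies before any scan without recorded progression. Wide intervals show that the estimate is imprecise; they do not offset a bias that runs one way.

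**Conclusion.** The concern holds in a conditional form. The response-evaluable rules contradict one another, both condition on post-baseline events, and the analysis section does not say which set is the denominator. Upward bias is a risk that follows from one reading of the text and is not an established feature of the analysis.

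Under the Section 8 reading, the factor is 1.00, 1.125, 1.29 or 1.50 for 0, 1, 2 or 3 early non-responders dropped from 9. This assumes that those dropped are all non-responders, which the assessment and confirmation schedule makes likely. The numbers of responders and early losses are assumptions.

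This should be fixed before response is analysed. It is not of the highest severity: the consequence is a biased descriptive estimate for a secondary endpoint with no test or threshold, and no error rate is affected. The SD interval conflict is a separate, minor inconsistency and adds no weight to this point.

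**What to change.** 1. Reconcile Sections 5.5, 8.1.2.3 and 8.2.2.2 to a single response-evaluable definition, and correct the Part B sentence so that the baseline and end-of-Cycle-2 assessments are named separately.
2. State in Section 10.3.4 that the primary response proportion uses all eligible patients who received at least one dose and had a baseline disease assessment. For Part B, add measurable disease, which Section 4.2.2 already requires at entry. Do not add that condition for Part A: Section 4.2.1 does not require it, so it could remove treated patients. The Appendix 5 statement that non-measurable-only disease is not allowed should be squared with Section 4.2.1 at the same time.
3. Count EP, death before the first scan, early stop without a documented response, and NE as non-response, each shown as its own row.
4. Report the evaluable-only proportion as a labelled sensitivity analysis.
5. Separately, reconcile the SD minimum interval in Appendix 5 (4 weeks) with the body of the protocol (6 weeks).

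The cost is protocol wording only, with no new visits, scans or patients. The one downside is that the headline response rate may come out slightly lower.

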8.2.2.3 Biomarker assessment

The samples and schedule for biomarker assessment will be the same in Part B as in Part A, with the exception that there will be no PBMC biomarker blood sampling. See section 8.1.2.4 for full details. A summary of the samples and time points is shown in the Table 11 below. The specific timing of these biopsies and blood samples may be adjusted later if the emerging PK and PD data suggest an alternative time point would be more informative.

Table 11: Details of research samples and schedule: Part B

Site	Sample	Pre-treatment	C2D1 (± 3 days)	C4D1 (± 3 days)	C6D1 (± 3 days)	Every 2 cycles thereafter (i.e. C8D1 etc)	At disease progression
Christie	Tumour Biopsy	x ¹	x ²	-	-	-	x ²
	CTC Sample (1x 10ml CellSave)	x	x	x	x	x	x
	cfDNA/ Genomic Sample (1x 10ml CellSave)	x	x	x	x	x	x
	CDX Sample (1x 10ml EDTA)	x	-	-	-	-	-
Royal Marsden	Tumour Biopsy	x ²	x ²	-	-	-	x ²
	Blood Sample (2x 10ml CellSave)	x	x	x	x	x	x

¹ Tumour sample will be split in three; a third of the biopsy will be snap frozen in liquid nitrogen and stored at -80°C, a third of the biopsy will be fixed in formalin and a third of the biopsy will be taken to the Molecular Oncology lab for further processing and implanting subcutaneously in immunodeficient mice for the establishment and the development of patient-derived xenografts. If only a small sample is obtained that cannot be split, the entire sample will be snap frozen

² Half of the biopsy will be snap frozen in liquid nitrogen and stored at -80°C, and the other half will be fixed in formalin. If only a small sample is obtained that cannot be split, the entire sample will be snap frozen

8.2.3 Off-study evaluations

These must be performed 28 days (± 3days) after the last dose of CCT3833, and should include the following at a minimum:

- Assessment of AEs and concurrent medications.
- ECOG Performance status.

- Physical examination and weight.
- Vital signs.
- Blood tests (including for tumour markers).
- ECG.
- Radiological/Clinical disease assessment.
- Subsequent tumour biopsy – optional.

8.2.4 Subsequent follow-up

In Part B (the expansion stage), a case report form entry should be completed at each hospital visit until objective disease progression has been recorded, or a maximum total of 12 cycles of treatment have been delivered, whichever occurs first. Responding patients may continue to receive treatment on a compassionate basis beyond 12 cycles.

Any patients who have ongoing treatment-related toxicities will be followed up on a monthly basis until resolution to baseline or stabilisation of symptoms, unless another anti-tumour treatment is started.

Once treatment has been completed, patients will be followed up for 12 months, for survival status only. This will be conducted via telephone interviews.

Table 12: Study flow chart- Dose escalation phase

[figure not shown]

Table 13: Study flow chart- Dose expansion phase

[figure not shown]

Table 14: Schedule of events- Dose escalation stage

Observation/Investigation	Pre-study		First dose for PK	Standard evaluations for each cycle of CCT3833; 1 cycle = 28 days						Off study (± 3 days)	Follow up (for AE until resolution) Monthly
	Between Day -28 and first PK dose	Between Day -7 and first PK dose		Cycle 1, Day 1 (± 1day)	Day 8 (±1day)	Day 15 (±1day)	Weekly thereafter until C3D1 (± 1day)	Fortnightly thereafter until C5D1 if no DLT observed (± 1day)	Monthly thereafter if no DLT observed (± 1day)		
Written informed consent	x										
Demographics and height	x										
Medical history	x										
Availability of historical tumour biopsy	x										
Radiological assessment ^a	x			At end of every 2 cycles on a stable dose							
Clinical disease assessment (if applicable)		x		At end of every cycle						x	
AE evaluation	x		x	x	x	x	x	x	x	x	x ^k
Concurrent medications	x		x	x	x	x	x	x	x	x	
Urinalysis (bHCG) ^b		x									
Tumour serum markers (if applicable)		x		At end of every cycle						x (unless performed within previous 6 weeks)	
Optional tumour biopsy ^c	x						x (C2D1 only)			x	
Optional CTC/genetics research blood sample ^d	x			x (C2D1) and thereafter every 2 cycles (i.e. C4D1, C6D1 etc)						x	
Optional PBMC research blood sample ^e			x				x (C2D1 only)				
ECOG performance status (Appendix 2)	x	x	x	x	x	x	x	x	x	x	
Physical examination ^f		x	x	x					x	x	
Weight		x	x	x					x	x	
Vital signs ^g : temperature, pulse, BP, oxygen saturation		x	x	x	x	x	x	x	x	x	
Laboratory tests ^h		x		x	x	x	x	x	x	x	x ^k
ECG		x	x	x	x	x	x	x	x	x	
Echocardiogram ⁱ (±3 days)	x						x (C2D1)				

Blood for PK assays ¹			x				x (C2D1)				
----------------------------------	--	--	---	--	--	--	----------	--	--	--	--

- a) Radiological assessment using CT or MRI as appropriate.
- b) If the patient is a woman of child bearing potential.
- c) Tumour tissue needle biopsies (10mg material required) for pharmacodynamics assessment will be optional for patients in Part A (dose escalation stage). The sampling timepoints will be pre-dose between Day -28 and the first dose for PK between Day-7 and -3 and at C2D1 (± 3 days), and when the patient is withdrawn from treatment.
- d) Research blood samples for circulating tumour cell collection (2-3 x 10mL) will be requested (optional) from patients in Part A (dose escalation stage). The sampling points will be pre-dose between Day -28 and the first dose for PK (between Day-7 and Day -3), at Cycle 2 Day 1 (± 3 days) and thereafter every 2 cycles (i.e. Cycle 4 Day 1, Cycle 6 Day 1 etc), and when the patient is withdrawn from treatment.
- e) Research blood samples for PBMC collection (4-5 x 5ml) will be requested (optional) from patients in Part A (dose escalation stage). The sampling time points will be alongside the PK blood samples: namely pre-dose and following single dose administration (on Day -7 to Day -3) at 4, 8, 24 and 48 hours post-dose, and alongside the PK blood samples on Cycle 2, Day 1 (± 3 days) at 0, 4, 8, 24 hours post-dose.
- f) Complete physical examination to be performed pre-study, then all examinations can be symptom-directed performed on Day 1 of each cycle
- g) Temperature, pulse rate, blood pressure and oxygen saturation rate should be performed pre-dose and then repeated every 30 mins (± 5 min) for the first 4 hours post-dose at the first dose for PK (between Day-7 to -3). Vital signs should be repeated each week of Cycles 1 and 2, and then on D1 and D15 from Cycle 3 onwards at the discretion of the Investigator, and reduced again to once a month from Cycle 5 onwards.
- h) Laboratory tests will be performed alongside each clinical visit; clinical laboratory assessments should therefore be performed on Days 1, 8, 15, 22 during Cycles 1 and 2. The frequency can be reduced to Days 1 and 15 from Cycle 3 onwards at the discretion of the Investigator, and reduced again to once a month (pre-dose on Day 1) from Cycle 5 onwards. In the event of a grade 4 neutropenia or grade 4 thrombocytopenia, a full blood count must be performed at least on Day 5 after the onset of the event to determine if a DLT has occurred. Continue close monitoring until resolution to grade 3 or less. Non fasting glucose, and LDH are required for biochemistry. If non fasting glucose >7.8 mmol/l, repeat as a fasting glucose. If this too demonstrates grade 3 hyperglycaemia, a formal glucose tolerance test should be undertaken, and appropriate management of hyperglycaemia initiated.
- i) An echocardiogram will be performed pre-study and at the start of Cycle 2 (± 3 days). It will then only be repeated as clinically indicated.
- j) 4 mL blood samples for PK assessment will be taken for all patients between Day-3 and Day-7, and on C2D1 at twelve time points: pre-dose on the day of dosing, 15 min (± 5 min), 30 min (± 5 min), 1 h (± 5 min), 1.5 h (± 10 min), 2 h (± 10 min), 3 h (± 10 min), 4 h (± 15 min), 6 h (± 15 min), 8 h (± 15 min), 12 h (± 60 min), 24 h (± 120 min) and 48 h (± 120 min; Day -7 to Day -3 admission only) post-dose. The same C2D1 sampling schedule will be used for patients that are dose escalated on C2D1 of the increased dose
- k) Monthly follow-up only required for those AEs and SAEs considered drug-related (highly probably, probably, or possible) that are present at time patient ends the study. Monthly follow-up to continue until resolution to baseline, stabilisation or patient starts another anticancer treatment.

Table 15: Schedule of events- Dose expansion stage

Observation/Investigation	Pre-study		Standard evaluations for each cycle of CCT3833; 1 cycle = 28 days				Off study	Follow up (for AE until resolution)
	Between Day -28 and Cycle 1	Between Day -7 and Cycle 1	Cycle 1, Day 1 (± 1day)	Day 15 (± 1day)	Cycle 2, Day 1 (± 1day)	Monthly thereafter if no DLT observed (± 1day)	(± 3 days)	Monthly
Written informed consent	x							
Demographics and height	x							
Medical history	x							
Availability of historical tumour biopsy	x							
Radiological assessment ^A	x		At end of every 2 cycles				x	
Clinical disease assessment (if applicable)		x	At end of every cycle				x	
AE evaluation	x		x	x	x	x	x	x ^I
Concurrent medications	x		x	x	x	x	x	
Urinalysis (bHCG) ^B		x						
Tumour serum markers (if applicable)		x	At end of every cycle				x (unless performed within previous 6 weeks)	
Optional tumour biopsy ^C	x				x		x	
Optional CTC/genetics research blood samples ^D	x				x (and every 2 cycles thereafter)		x	
ECOG performance status (Appendix 2)	x	x	x	x	x	x	x	
Physical examination ^E		x	x	x	x	x	x	
Weight		x	x		x	x	x	
Vital signs ^F : temperature, pulse, BP, oxygen saturation		x	x	x	x	x	x	
Laboratory tests ^G		x	x	x	x	x	x	x ^I

ECG		x	x	x	x	x	x	
Echocardiogram ^H (±3 days)	x				x			

- A. Radiological assessment using CT or MRI as appropriate. Baseline assessment to include MRI brain; only to be repeated if evidence of brain metastases at baseline or in response to new symptoms.
- B. If the patient is a woman of child bearing potential
- C. Tumour tissue needle biopsies (10mg material required) for pharmacodynamics assessment will be optional for patients treated in Part B (expansion cohorts). The three sampling points will be pre-dose between Day -28 and C1D1, during treatment on C2D1 (± 3 days), and at disease progression.
- D. Research blood samples for circulating tumour cell collection (2-3 x 10mL) will be requested (optional) from patients in Part B (dose expansion stage). The sampling points will be pre-dose between Day -28 and Cycle 1, day 1, at Cycle 2 Day 1 (± 3 days), and every 2 cycles thereafter (i.e. Cycle 4 day 1, Cycle 6 day 1 etc) and when the patient is withdrawn from treatment.
- E. Complete physical examination to be performed pre-study, then all examinations can be symptom-directed performed on Day 1 of each cycle
- F. Temperature, pulse rate, blood pressure and oxygen saturation rate should be performed at each clinical visit.
- G. Laboratory tests will be performed alongside each clinical visit; clinical laboratory assessments should therefore be performed on Days 1, and 15 during Cycle 1 and then reduced to once a month (pre-dose on Day 1) from Cycle 2 onwards. In the event of a grade 4 neutropenia or grade 4 thrombocytopenia, a full blood count must be performed at least on Day 5 after the onset of the event to determine if a DLT has occurred. Continue close monitoring until resolution to grade 3 or less. Non fasting glucose and LDH are required for biochemistry. If non fasting glucose >7.8 mmol/l, repeat as a fasting glucose. If this too demonstrates grade 3 hyperglycaemia, a formal glucose tolerance test should be undertaken, and appropriate management of hyperglycaemia initiated.
- H. An echocardiogram will be performed pre-study and at the start of Cycle 2 (± 3 days). It will then only be repeated as clinically indicated.
- I. Monthly follow-up only required for those AEs and SAEs considered drug-related (highly probably, probably, or possible) that are present at time patient ends the study. Monthly follow-up to continue until resolution to baseline, stabilisation or patient starts another anticancer treatment.

